8.0 TREATMENT PLAN

8.1 Randomization

Three-month supplies will be provided for each patient for the duration of the intervention. Careful instructions regarding medication administration will be provided verbally, and patients will be instructed call or visit the clinic or call the research team at any time if necessary.

8.2 Study Intervention Schedule

Agent	Dose	Route	Interval
Eflornithine placebo	2 tablets	Oral	Daily for 18 months
Or			
Eflornithine*	2 tablets	Oral	Daily for 18 months

*Each eflornithine tablet is 250mg

Initial Visit (pre-randomization): Patient should have history and physical, weight, and blood draw (include CBC: Hgb, hematocrit, WBC, platelets; liver tests: bilirubin, AST, ALT; and creatinine). Additionally, women of child bearing potential will have a pregnancy test (serum or urine) within 14 days prior to start of study drug. Patients will be evaluated via endoscopy at baseline. Audiometry testing to document air conduction will be conducted.

Follow-up during intervention (Months 0-18): During the 18 month intervention, patients will be followed at three month intervals with clinic visits which include a physical exam and blood draw (CBC, chemistries). Endoscopic surveillance is incorporated into the follow up at 6 and 18 months. Study drug dispensation coincides with clinic visits. More frequent patient contact is planned (e.g., phone follow-up: weekly in months 0-6, and monthly thereafter), at the discretion of the site investigator, in consultation with the study PIs, as in prior clinical trials.[59,60]

Final intervention visit (Month 18): At Month 18, all patients will have a complete physical exam, blood draw (CBC, chemistries), and pure tone audiogram.

Post intervention follow-up (Month 24): All patients will be followed for 6 months after completion of the 18 months of intervention off of study medications.

Patient removal from protocol: If the patient terminates the protocol intervention between completion of Month 3 and Month 18, the complete physical exam, blood draw (CBC, chemistries), pure tone audiogram, and endoscopy will be

offered to the patient at that time. If the patient terminates the protocol intervention prior to Month 3, the physical exam, blood draw (CBC, chemistries), and pure tone audiogram are recommended, without endoscopy. Endoscopy will be offered to the patient at Month 24 as part of usual care and clinical surveillance protocol at the sites for subjects with premalignant lesions.

8.3 Endoscopy Procedures (Months 0, 6, 18, 24):

The endoscopy with standard biopsies of the gastric mucosa will be done at four time points: Months 0 (pre-study), 6, 18, and 24. Patients are screened at the time of the index endoscopy, previously scheduled for clinical indications per local standard of care. Samples obtained at the time of the index endoscopy performed per standard of care prior to informed consent for this study may be submitted for research once informed consent is obtained. The Month 0 (pre-study) and Month 24 endoscopies are part of usual care clinical screening and surveillance endoscopies in high risk regions, per local and emerging international standards.[61] The allowable timeframe for each endoscopy is - 30/+60 days. The gastric mapping biopsy protocol for histology follows the international protocols,[61] and with additional research biopsies per longstanding protocol. (Appendix 16.2).

Biopsy mapping of the gastric mucosa for histopathology is part of usual care of patients at study sites, and adherent to emerging international standards for stomach precancerous lesions. Five formalin-fixed biopsies are obtained from the antrum (2), corpus (2), and incisura (1). Two sets of research small pinch biopsies are obtained for the study, preserved for study analyses.

The potential risks of endoscopy include perforation, bleeding, infection, and drug reaction. Biopsies of the stomach are considered a routine component of diagnostic upper endoscopy. The serious adverse event rate for upper endoscopy with biopsies is less than 1/6000 cases (<0.02%).[62] Perforation and bleeding may require a repeat endoscopy, and in some cases, surgery. Infection at the biopsy sites is highly unlikely. Allergic reactions to medications used for procedure sedation are extremely uncommon, and would be treated immediately if they should occur.

8.4 Patient Pill Diary and Pill Dispensing

A pill diary will be provided for patient use to facilitate tracking and adherence of the assigned intervention. Three-month supplies of study drug are issued throughout the intervention.

8.5 Adherence/Compliance

Adherence to the blinded drug in this study will be measured by returned tablet count. All unused study medication is returned to the clinic at each follow-up assessment every 3 months. The remaining tablets are counted and the number of pills dispensed and returned will be documented. An individualized adherence intervention strategy is used when the adherence level is below 75%. The Coordinating Center [REDACTED] should be notified within 7 days whenever an intervention strategy needs to be implemented for a patient. The following information should be included in this notification:

- Protocol Number
- Subject ID
- % compliance noted
- Intervention strategy implemented

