Pregnancy and Lactation: Eflornithine is contraindicated in women who are or may become pregnant and in nursing mothers. It is likely that eflornithine will cause fetal harm when administered to pregnant women. Eflornithine has been shown to have a contragestational effect in mice, rats, and rabbits, when given in doses equivalent to approximately fifty-times the dose used in human chemoprevention trials. If this drug is used during pregnancy, or if the patient becomes pregnant while taking this drug, the patient should be apprised of the potential hazard to the fetus. Eflornithine is also contraindicated in patients who are hypersensitive to eflornithine or any of the inactive ingredients.

c. PHARMACOLOGY

Kinetics: Therapeutic drug concentration is not established. Time to peak concentration for oral eflornithine is 4-6 hours. Absorption: for the oral solution is 54-58% and is unaffected by feeding status. Distribution: no protein binding sites, crosses blood-brain barrier. Volume of distribution is 0.3-0.35 liters/kg.

Metabolism: urinary recovery of unchanged drug as eflornithine is 86% and essentially not metabolized. Excretion: renal excretion. Elimination half-life: 3-3.5 hours but once daily dosing is sufficient to maintain efficacy.

Formulation: Eflornithine 250 mg and placebo are supplied as tablets.

Composition of Eflornithine: The active compound is DFMO (as the monohydrate monohydrochloride monohydrate) (Eflornithine HCl) 250 mg; with microcrystalline cellulose, starch 1500, silicon dioxide, magnesium stearate and opadry.

Composition of Eflornithine placebo: Dibasic calcium phosphate dihydrate, microcrystalline cellulose, starch 1500, hypromellose, silicon dioxide, magnesium stearate, opadry (yellow).

Storage and Stability: Tablets are stored at room temperature.

Administration: Two tablets by mouth daily taken with food. The tablets are a light tan color.

Supplier: Eflornithine and placebo will be supplied by Cancer Prevention Pharmaceuticals, Tucson, AZ, USA.

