3.2 Agent Supply and Labeling

Eflornithine 250 mg tablets and matching placebo will be provided free of charge by Cancer Prevention Pharmaceuticals (CPP). CPP will provide eflornithine and placebo to Sharp Clinical Services, Inc., who will then label and distribute to the study sites.

Eflornithine and matching placebo will be supplied in white plastic bottles with a child resistant cap and tamper evident seal, each containing 100 tablets of either 250 mg eflornithine or matching placebo.

Each bottle will be labeled with:

- The protocol number
- The patient study number (e.g., "999999")
- The number of tablets (e.g., "100 tablets")
- The agent identification (e.g., "eflornithine 250 mg or placebo")
- Administration instructions (i.e., "2 tablets once a day")
- The date (year, month, day as xxxx.yy.zz)
- The bottle labels will have a line for the patient initials

The convention for patient initials and names is "ABCD" for which A represents the first name, B is the second (middle) name, C is the first surname, and D is the second surname (if used by the patient).

- The lot number (e.g., “9999”)
- The caution information (e.g., “Keep out of reach of children”)
- The storage information (e.g., temperature range)
- The clinical study restriction (e.g., “For clinical study use only”)
- The sale information (e.g., “Not for sale”)
- The study contact information (e.g., Investigator, Sponsor, Distributor)

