9.0 TOXICITIES TO BE MONITORED AND DOSAGE MODIFICATIONS

9.1 This study will utilize the CTCAE version 4.0 (NCI Common Terminology Criteria for Adverse Events) for toxicity and Serious Adverse Event (SAE) reporting.

9.2 Guidelines for monitoring expected and unexpected symptoms/toxicities are defined below.

All interventions can be dose reduced based on toxicity or participant perceived toxicity. All toxicities are recorded on the Adverse Events Summary Form. All patients who discontinue treatment after randomization will continue to be followed for endoscopy results.

Guidelines for Monitoring of Expected and Unexpected Symptoms/Toxic Events:

- **Grade 0**
No monitoring necessary.
- **Grade 1 and Grade 2**
Monitor as needed until problem has resolved (i.e., Grade 0), stabilized (i.e., remains as Grade 1 or Grade 2), or is otherwise explained. If Grade 1 or Grade 2 symptoms persist, the physician will assess whether study medication is to be discontinued or whether symptom management should be initiated.
- **Grade 3 and Grade 4 Toxicities:**
If any Grade 3 or Grade 4 toxicity occurs, ascertain cause of event and study relatedness. If symptoms are related to the study drug, the dose of the drug should be reduced by 50% as follows:

Study Drug	50% Dose Reduction	Frequency	If toxicity improves to grade 0, 1, or 2
Eflornithine or matched placebo	250 mg (1 tab)	Daily	Continue dosing at 50%

If Grade 3 or 4 toxicity persists at 50% dose level, the patient can be given a 4 week drug holiday. After the 4 week drug holiday, the patient may be re-challenged at the aforementioned 50% dose reduction level for 4 weeks. Patient will be removed from protocol treatment if there is a cumulative delay of study intervention >90 days.

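### After a dose reduction the specified bottle label still gives the full-dose instruction, and the tablet-count rule cannot identify over-use because it has only a lower trigger and no defined denominator

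*Combined protocol and SAP*

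**What the plan says.** **Regimen and label.** Section 3.1 gives the regimen: "Two tablets by mouth daily taken with food". Section 3.2 specifies 100-tablet bottles whose printed instruction is "2 tablets once a day". An outside company labels and distributes them.

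**Dose reduction.** For Grade 3 or 4 toxicity, section 9.2 says "If symptoms are related to the study drug, the dose of the drug should be reduced by 50% as follows". The table that follows gives 1 tablet (250 mg) daily and keeps the patient there once the toxicity improves. If it persists, a four-week drug holiday may be given, followed by re-challenge at the reduced level. Section 9.2 also opens reduction to toxicity that the participant perceives.

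**Adherence.** Section 8.5 says "Adherence to the blinded drug in this study will be measured by returned tablet count", that "All unused study medication is returned to the clinic at each follow-up assessment every 3 months", and that "The remaining tablets are counted and the number of pills dispensed and returned will be documented". It has one trigger: "An individualized adherence intervention strategy is used when the adherence level is below 75" per cent. The Coordinating Center is then told within 7 days. The notice has four items: protocol, subject, compliance percentage and strategy used.

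**Supply.** Sections 8.1 and 8.4 provide three-month supplies without saying at which daily dose. No section mentions relabelling or a different quantity after a reduction.

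**The concern.** Two stated rules meet badly in the patients whose dose has been cut. The only printed instruction the plan specifies for the bottle is the full-dose one, although section 9.2 has prescribed half of it. The monitoring rule that might catch the mismatch looks only for too few tablets taken.

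Section 8.5 also does not say what the tablets taken are divided by, and does not mention reductions or holidays. The same behaviour can be reported as poor or perfect adherence, and the compliance percentage sent to the Coordinating Center carries no dose level with which to interpret it.

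At stake are the detection of dosing above the prescribed level after related toxicity, and the meaning of the adherence record.

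**Working it through.** **Inputs.** Full regimen 2 tablets a day (3.1, 3.2); reduced regimen 1 tablet a day (9.2); bottle of 100 tablets (3.2); holiday of 4 weeks = 28 days (9.2); trigger below 75%, with no upper limit (8.5). The three-month count interval is taken as 91 days; 90 or 92 days moves results by at most about one percentage point.

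**Consistency check.** 50% × (2 × 250 mg) = 250 mg = 1 tablet, so the reduction table agrees with itself. The 75% is a chosen threshold with no derivation to reproduce.

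**Formula.** Adherence = (dispensed − returned) / denominator. Section 8.5 gives the numerator but no denominator, so each plausible one is tried.

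**Whole interval at the reduced dose**

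| Supply issued | Denominator | Obeys, 1/day | Keeps taking 2/day |
|---|---|---|---|
| Full-dose | Labelled dose, 182 | 91/182 = 50.0%, flagged | 182/182 = 100%, passes |
| Two bottles | Dispensed, 200 | 91/200 = 45.5%, flagged | 182/200 = 91.0%, passes |
| Full-dose | Prescribed dose, 91 | 91/91 = 100%, passes | 182/91 = 200%, passes |
| One bottle | Dispensed, 100 | 91/100 = 91.0%, passes | 100/100 = 100%, passes |
| One bottle | Labelled dose, 182 | 91/182 = 50.0%, flagged | 100/182 = 54.9%, flagged as low |
| One bottle | Prescribed dose, 91 | 91/91 = 100%, passes | 100/91 = 109.9%, passes |

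In the one-bottle rows the patient taking 2 a day runs out after 100/2 = 50 days. In the right-hand column, no row identifies excess as excess; the single flag there reports under-use.

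**Holiday of 28 days, 1 tablet a day otherwise.** Tablets taken = 91 − 28 = 63. Against the label, 63/182 = 34.6%; against two bottles, 63/200 = 31.5%; against the prescribed 1 a day without removing holiday days, 63/91 = 69.2%. All are flagged. With holiday days removed, 63/63 = 100%.

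**Reduction starting on day t of an interval.** An obedient patient takes 2t + (91 − t) = 91 + t tablets. Against 182, the flag needs 91 + t < 136.5, so t < 45.5. Against 200, it needs 91 + t < 150, so t < 59. In that interval the flag depends on timing as well as on the denominator.

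**What correcting the denominator alone would do.** The obedient patient scores 100%. The over-user with a full-dose supply scores 200% and still passes, so an upper flag is needed too.

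**The case against.** A reader might infer that the rule works backwards: that it does flag the patient who obeys the reduction, presses that patient to take more drug, and makes the eflornithine arm look less adherent. The documents do not support this.

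- The denominator is undefined. A site counting against the prescribed dose, or dividing by one dispensed bottle, scores the obedient patient at 91% to 100%.
- The strategy is individualized, and sites manage reductions themselves, so staff would ordinarily know of one. Nothing tells them to urge tablets beyond the prescription.
- The tablet count is not the only contact. A pill diary is reviewed at each visit (section 10.0, note 2), phone contact is planned at the centres' discretion (note 7), and administration instructions are given verbally (section 8.1).
- Section 12.1 uses adherence in no endpoint, covariate or per-protocol set, and section 8.6 specifies intent-to-treat. The documents give no reduction rate, and section 2.0 calls toxicity modest.
- Section 8.5 is silent about reductions rather than in contradiction with them.

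All of this stands, and it limits the point. It does not remove it. The label instruction and the reduced regimen still conflict. Note 7 equates the adherence assessment with the pill count, so the diary is outside the measure. Verbal instructions are not tied to a dose change. The 100% and 91% scores for over-use assume a full-dose supply, but a smaller supply does not make the rule recognise over-use either.

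**Conclusion.** The point holds in three parts. First, the specified label conflicts with the prescribed regimen after a reduction, and no step resolves it. Second, the trigger is one-sided: a patient on 2 tablets a day after reduction scores 91% to 200% with a full-dose supply, and is not identified as over-using under any denominator tried. Third, the obedient patient can be flagged (45.5% to 50%) or not (91% to 100%) depending on unwritten site practice, and a permitted holiday gives 69.2% even against 1 tablet a day.

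These figures assume a 91-day interval spent wholly at the reduced dose, apart from the holiday. The number of patients affected cannot be estimated from the documents. The consequence is for safety oversight and the adherence record. The primary analysis and sample size are untouched. No view is taken on which dose or toxicity rule is right.

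**What to change.** Reconcile sections 3.2, 8.4, 8.5 and 9.2, leaving every dose rule as it is:

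1. **Sections 3.2, 8.4 and 9.2:** when the prescribed dose changes, update the label instruction and the quantity dispensed, identically in both arms. Section 9.2 already applies reductions to drug and matched placebo alike, so this need not unblind anyone.
2. **Section 8.5, definition:** adherence = tablets taken / tablets prescribed at the dose level in force on each day, excluding protocol holiday days.
3. **Section 8.5, upper flag:** add an over-use flag with a small stated tolerance above 100%. The tolerance is needed because one lost tablet at 1 a day already gives 92/91 = 101.1%.
4. **Coordinating Center notice:** add current dose level and holiday days, so the reported percentage can be read.

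The cost is wording in four sections, one relabelling step per dose change and two data fields.

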8.6 Study Blinding Information and Criteria for Removal from Protocol Treatment

- a. All patients, study centers, pathology and laboratory personnel will be blinded to study treatment. The study pharmacist at each study site is unblinded to facilitate randomization.
- b. Laboratory and pathology specimens will be labeled by patient identification number and initials only.
- c. The study drug may be discontinued without unblinding the patient. Patient's treatment will be unblinded only if the treating physician demonstrates a compelling medical need for this information (Appendix).
- d. As study arms will be analyzed using an intent-to-treat method, patients are never "dropped" from the study.

- e. Patients will be removed from protocol treatment under the following circumstances, and all reasons for discontinuation will be documented:
 - Unacceptable toxicity (Section 8.0).
 - A patient who becomes pregnant or declines contraception.
 - Intercurrent illness which would affect assessments, in the opinion of the treating physician.
 - Cumulative delay of study intervention >90 days for any reason.
 - The patient may withdraw from the study at any time for any reason.

9.0 TOXICITIES TO BE MONITORED AND DOSAGE MODIFICATIONS

9.1 This study will utilize the CTCAE version 4.0 (NCI Common Terminology Criteria for Adverse Events) for toxicity and Serious Adverse Event (SAE) reporting.

9.2 Guidelines for monitoring expected and unexpected symptoms/toxicities are defined below.

All interventions can be dose reduced based on toxicity or participant perceived toxicity. All toxicities are recorded on the Adverse Events Summary Form. All patients who discontinue treatment after randomization will continue to be followed for endoscopy results.

Guidelines for Monitoring of Expected and Unexpected Symptoms/Toxic Events:

- **Grade 0**
No monitoring necessary.
- **Grade 1 and Grade 2**
Monitor as needed until problem has resolved (i.e., Grade 0), stabilized (i.e., remains as Grade 1 or Grade 2), or is otherwise explained. If Grade 1 or Grade 2 symptoms persist, the physician will assess whether study medication is to be discontinued or whether symptom management should be initiated.
- **Grade 3 and Grade 4 Toxicities:**
If any Grade 3 or Grade 4 toxicity occurs, ascertain cause of event and study relatedness. If symptoms are related to the study drug, the dose of the drug should be reduced by 50% as follows:

Study Drug	50% Dose Reduction	Frequency	If toxicity improves to grade 0, 1, or 2
Eflornithine or matched placebo	250 mg (1 tab)	Daily	Continue dosing at 50%

If Grade 3 or 4 toxicity persists at 50% dose level, the patient can be given a 4 week drug holiday. After the 4 week drug holiday, the patient may be re-challenged at the aforementioned 50% dose reduction level for 4 weeks. Patient will be removed from protocol treatment if there is a cumulative delay of study intervention >90 days.

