1.4 Number of patients with quantitative toxicities. Toxicities will be assessed per CTCAE criteria, and each toxicity will be assigned an adverse event (AE) term according to CTCAE definitions (each AE term = unique representation of a specific event used for medical documentation and scientific analyses), and graded as defined by CTCAE (grade 1 = mild; grade 2 = moderate; grade 3 = severe or significant but not immediately life-threatening; grade 4 = life-threatening; grade 5 = death).

1.5 To evaluate whether candidate single nucleotide polymorphisms (SNPs) relevant to eflornithine (DFMO) efficacy.

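### Section 9.2 gives drug-related Grade 4 toxicity the same half-dose first step as Grade 3, with no required hold or stop, and the unacceptable-toxicity removal criterion in 8.6e is not defined

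*Combined protocol and SAP*

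**What the plan says.** Section 1.4 adopts the CTCAE grades and states "grade 4 = life-threatening".

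Section 9.2 then sets out actions by grade. For the lower grades: "If Grade 1 or Grade 2 symptoms persist, the physician will assess whether study medication is to be discontinued"; the alternative named is symptom management. For Grade 3 and Grade 4 together, the site first establishes cause and relatedness. For a related event: "If symptoms are related to the study drug, the dose of the drug should be reduced by 50% as follows". The table gives one 250 mg tablet daily, continued at that level once the toxicity falls to Grade 0, 1 or 2. For toxicity that does not improve: "If Grade 3 or 4 toxicity persists at 50% dose level, the patient can be given a 4 week drug holiday". Then: "After the 4 week drug holiday, the patient may be re-challenged at the aforementioned 50% dose reduction level for 4 weeks". The paragraph closes: "Patient will be removed from protocol treatment if there is a cumulative delay of study intervention >90 days".

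Section 8.6e opens its list with "Patients will be removed from protocol treatment under the following circumstances", and the first item reads "Unacceptable toxicity (Section 8.0". Section 8.6c separately allows study drug to be discontinued without breaking the blind.

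**The concern.** A patient in a prevention trial who has a life-threatening event judged to be drug-related would normally have the drug held at once and, in most protocols, stopped for good. Here the first grade-specific step is to keep dosing at half strength. The next step presupposes a patient who is still taking 250 mg while Grade 3 or 4 toxicity is unresolved. The rule that should take precedence, removal for unacceptable toxicity, has no threshold. What is at stake is patient safety and consistency between sites, of which Section 7.1 allows up to three.

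**Working it through.** The plan states no figure on this point, so the check is mainly a comparison of text.

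**1. Follow a related Grade 4 event through 9.2.**
- First step: 500 mg to 250 mg daily, and 250/500 = 50%. No interruption is required while cause is being established.
- If it improves to Grade 0–2: stay at 250 mg.
- If it persists at 250 mg: a 4-week holiday is optional. No length of time is given for persistence.
- After the holiday: re-challenge at 250 mg is optional, at the dose at which the toxicity persisted.
- If it recurs on re-challenge: nothing is stated.

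No step separates Grade 4 from Grade 3.

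**2. Does the 90-day limit act as an early stop?** One holiday is 4 × 7 = 28 days. That leaves 90 − 28 = 62 days, and because the rule requires more than 90 days it is met on the 63rd further day. Three holidays total 84 days, and a fourth would bring 112. Section 9.2 does not say whether a holiday may be repeated. Delay is not defined; if days at half dose do not count as delay, which is an assumption, they never bring the limit closer. On any of these readings the limit is not an early safety stop.

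**3. Look for a definition of unacceptable toxicity.** Section 8.0 is the treatment plan (randomisation, schedule, endoscopy, pill diary, adherence, blinding) and has no toxicity criterion. The pointer looks like a one-section numbering slip, because other references are off by one in the same way:

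| Where | Refers to | Content now at |
|---|---|---|
| 4.3 | 6.2 and 6.3 (*H. pylori*) | 7.2 and 7.3 |
| Study calendar, note 8 | 6.0 (*H. pylori* treatment) | 7.3 |
| 8.3 | Appendix 16.2 (biopsy mapping) | 17.2 |

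Reading the pointer as 9.0 does not help: Section 9 neither uses nor defines the term. Section 15 covers reporting and gives no dosing instruction.

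**4. Compare the grades.** For persistent Grade 1–2 symptoms the physician must consider discontinuation. The Grade 3–4 text contains no such assessment, and the only stop it names is the 90-day limit.

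**5. Cost of a stop rule to the primary comparison.** Inputs from Section 12.1: 150 per arm and a hypothesised difference of 18%, which already allows for 10% loss to follow-up, so no further deduction is made. Assume that each eflornithine patient who stops loses the whole effect and still has a 6-month biopsy. With k such patients the difference becomes 18 × (150 − k)/150:
- k = 1: 18 × 149/150 = 17.88
- k = 3: 18 × 147/150 = 17.64
- k = 5: 18 × 145/150 = 17.40

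The values of k are illustrative, because the documents give no rate.

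**The case against.** A reader might infer that sites are told only to continue at half dose after a life-threatening event, or that they may not stop the drug. The documents do not support either reading. Continuation at 250 mg depends on improvement to Grade 0–2, and persistent toxicity has its own step, the optional holiday. Section 9.2 is written as guidance and itself foresees patients who discontinue. Section 8.6c permits stopping at any grade, and 8.6e makes removal mandatory once toxicity is judged unacceptable.

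Other controls exist. A life-threatening event is an SAE (15.4.2), reported to the Coordinating Center within 24 hours (15.5.2) and passed to the sponsor within a further 24 hours (15.5.5). The VICC monitoring committee can intervene in the study (15.2). Appendix 17.3 provides for unblinding after a severe or life-threatening reaction. It can also be argued that leaving the threshold to the physician is a legitimate choice, and that serious toxicity at 500 mg daily is unlikely: Section 2.0 calls toxicity modest, and the seizures described in Section 3.1 occurred at 15 g daily.

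These points rule out the stronger reading, and the last one limits the likely number of patients. They do not fill the gap. Permission to stop is not a criterion for stopping, and none of the reporting or oversight provisions gives a dosing rule for the individual patient. If physician judgement is intended, it is odd that the assessment of discontinuation is written for Grade 1–2 and not for Grade 3–4.

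**Conclusion.** The point holds as a safety weakness in a stated dosing rule and should be corrected. For related Grade 4 toxicity, 9.2 prescribes half-dose continuation first and requires neither a hold nor a stop. It is silent on recurrence at re-challenge, and the mandatory removal rule in 8.6e rests on an undefined term and a wrong cross-reference.

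The number of patients exposed to this cannot be estimated, because the documents give no rate of related Grade 4 events; it is expected to be small. A reader might also infer harm to the primary analysis. Nothing in the documents shows that, and the day counts above show only that the 90-day limit is not an early stop. The conclusion rests on the text alone and does not depend on how delay is defined or on whether 8.0 was meant to be 9.0.

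**What to change.** In 9.2, limit the reduction, holiday and re-challenge text to related Grade 3 toxicity, and add:

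*Study drug is held while the cause of any Grade 4 event is ascertained. Unacceptable toxicity includes, but is not limited to, Grade 4 toxicity possibly, probably or definitely related to study drug, and related Grade 3 or 4 toxicity that recurs on re-challenge at 250 mg; study drug is then stopped permanently. Endoscopy follow-up and intent-to-treat inclusion continue.*

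In 8.6e, change the reference from Section 8.0 to Section 9.2.

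Naming the attribution categories of 15.4.4 fixes what counts as related for a Grade 4 event. The non-exhaustive wording leaves room to remove a patient for, say, intolerable persistent Grade 2 toxicity. The follow-up sentence should stay explicit: 9.2 keeps patients who stop in endoscopic follow-up, but 8.2 recommends no endoscopy at the time of stopping for those who stop before Month 3 and offers one at Month 24.

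The cost is wording in two sections, with no added scheduled visits or tests. A few patients may stop drug early, with the slight intent-to-treat dilution calculated above.
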